9. PATIENT ACCOUNTING AND STUDY DISPOSITION

A complete accounting of patient participation in the study by analysis population will be presented in Table 9 entitled *Patient Accounting and Disposition* (All Screened Patients). The purpose of this table is to provide an accounting of patients from their entrance into the study through the final visit and to account for the evaluations of patients in the major analyses of efficacy and safety, including reasons for early study termination. The table will display the number of patients that were consented and the number and percentage of patients from the ITT and PP populations that:

- Enrolled (n/%)
- Underwent the study procedure (n/%)
- Evaluated at visit 1 (n/%)
- Evaluated at visit 2 (n/%)
- Evaluated at visit 3 (n/%)
- Evaluated at visit 4 (n/%)
- Follow-up Phone Call (n/%)

Listing 1 entitled *Patient Disposition* supports Table 9. This listing will be sorted by patient number and will include the reason the patient was a screen failure, if the patient was not enrolled.

10. PROTOCOL DEVIATIONS AND VIOLATIONS

In accordance with ICH E3, Sponsor-defined eligibility and important post-dosing protocol deviations will be identified and listed separately by patient. Deviation type/code provided by the Sponsor will be used to classify the events as:

- Informed consent
- Randomization error
- Safety
- Efficacy
- Other protocol deviations

A listing and tabulation of protocol deviations will be provided in Listing 2 entitled *Protocol Deviations and Violations*. The listing will be sorted by patient number and date of the protocol violation.

11. BASELINE PATIENT DATA

11.1. Baseline Demographic Factors

All patients in the Safety Population will be included in summary of demographic information using descriptive statistics as described in Section 8 and the data variables as described in the TLF, Table 11.

11.2. Urogenital History

LUTS Symptoms during the prior 6 months will be tabulated using descriptive statistics as described in Section 8 and the data variables as described in the SRS TLF, Tables 12 and 13.

11.3. Medical History

Data will be summarized and tabulated using descriptive statistics as described in Section 8 and the data variables as described in the SRS TLF, Table 14.

11.4. Medications at Screening

Data will be summarized and tabulated using descriptive statistics as described in Section 8 and the data variables as described in the SRS TLF, Table 15.

11.5. Physical Examination and Vital Signs

A physical examination will be performed for all patients at the screening visit. The results will be presented as described in the SRS TLF, Table 16.

11.6. Digital Rectal Examination

Each patient will undergo a digital rectal examination at visit 1 screening. Data will be summarized and reported in Table 17 as described in the SRS TLF.

11.7. Clinical Laboratory Results

Each patient will have a panel of physiological assays at Screening. Data will be summarized and reported in Table 18 as described in the SRS TLF.

11.8. Catheterization Status (Prior to Procedure)

Data will be summarized and tabulated using descriptive statistics as described in Section 8 and the data variables as described in the SRS TLF, Table 19.

11.9. Cystoscopy: Bulbar Urethra Distal to External Sphincter

Data will be summarized and tabulated using descriptive statistics as described in Section 8 and the data variables as described in the SRS TLF, Table 20.

11.10. Cystoscopy: Verumontanum to Bladder

Data will be summarized and tabulated using descriptive statistics as described in Section 8 and the data variables as described in the SRS TLF, Table 21.

11.11. Cystoscopy: Bladder Status

Data will be summarized and tabulated using descriptive statistics as described in Section 8 and the data variables as described in the SRS TLF, Table 22.

12. PROCEDURE AND DEVICE ACCOUNTABILITY

12.1. Measurements with the Surveyor

Data will be summarized and tabulated using descriptive statistics as described in Section 8 and the data variables as described in the SRS TLF, Table 23.

12.2. Spanner Selected

Data will be summarized and tabulated using descriptive statistics as described in Section 8 and the data variables as described in the SRS TLF, Table 24.

12.3. Spanner Insertion

Data will be summarized and tabulated using descriptive statistics as described in Section 8 and the data variables as described in the SRS TLF, Table 25.

12.4. Spanner Removal

Data will be summarized and tabulated using descriptive statistics as described in Section 8 and the data variables as described in the SRS TLF, Table 26.

12.5. Urine Drainage Device Used at Study after Spanner

Data will be summarized and tabulated using descriptive statistics as described in Section 8 and the data variables as described in the SRS TLF, Table 27.

12.6. Spanner Accountability

Data will be summarized and tabulated using descriptive statistics as described in Section 8 and the data variables as described in the SRS TLF, Table 28.

12.7. Surveyor Accountability

Data will be summarized and tabulated using descriptive statistics as described in Section 8 and the data variables as described in the SRS TLF, Table 29.

12.8. Device Deficiencies

Data will be summarized and tabulated using descriptive statistics as described in Section 8 and the data variables as described in the SRS TLF, Table 30.

13. EFFICACY

This section will discuss the tabulation and analysis of the study objectives. Detailed descriptions of the statistical procedures that will be used to analyze the study endpoints will be described below.

13.1. PVR Summary Statistics

Data will be summarized and tabulated using descriptive statistics as described in Section 8 and the data variables as described in the SRS TLF, Table 31.

13.2. Primary Effectiveness Endpoint Analysis

The results of the Primary Effectiveness Endpoint analysis will be presented in the SRS TLF, Table 31.

The primary effectiveness endpoint for this study is the proportion of patients who achieve adequate bladder drainage over 90 days, defined as a post-void residual (PVR) of ≤ 150 ml. The pre-specified success criterion for this study is that ≥ 50 percent of patients will achieve adequate bladder drainage at each of the 4 evaluations over 90 days. The primary objective will be met if the one-sided lower bound of the 95% confidence limit for the incidence of patients who achieve adequate bladder drainage at each of the 4 evaluations over 90 days is $\geq 50\%$. The null and alternative hypotheses are as follows:

$$H_0: \pi \leq 0.5$$

$$H_a: \pi > 0.5$$

π is the proportion of patients with maintenance of successful voiding during the Spanner implantation period.

Results based on the ITT population will be presented in Table 32 entitled *Primary Effectiveness Endpoint Analysis* (PVR of ≤ 150 ml) (ITT population). The table will contain the point estimate and the confidence limit based on patients who met the primary endpoint.

13.3. Secondary Effectiveness Endpoints Analyses

The results of the Primary Effectiveness Endpoint analysis will be presented in the SRS TLF, Table 33.

The second effectiveness endpoints for this study are all based on the proportion of patients who achieve adequate bladder drainage at different PVR thresholds.

- PVR of ≤ 150 ml over 30 days.
- PVR of ≤ 250 ml over 30 days.
- PVR of ≤ 250 ml over 90 days.

13.4. Analysis of the Exploratory Effectiveness Endpoints

The results of the Exploratory Effectiveness Endpoint analysis will be presented as described in the SRS TLF, Tables 34 through 39. These include summary statistics (as described in Section 8) of the Qmax, IPSS, and QoL results. Both the ITT and PP groups will be described.

14. SAFETY

The following sections describe how the safety results (adverse events) will be summarized. All safety results will be presented using the Safety population.

14.1. Adverse Events Classification

14.1.1. Reporting of Adverse Events

The following information regarding each AE will be obtained: date and time of onset and resolution (duration), severity (defined below), whether it was serious, any required treatment or action taken, outcome, relationship to the investigational device, whether anticipated or unanticipated per protocol definition.

The definitions of seriousness, severity, relationship to device, and outcome are provided in the SRS Protocol.

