14.6 Safety Variables

Safety variables that will be recorded are:

- Treatment emergent adverse events deemed to be related to the implantation procedure

CONFIDENTIAL

- Treatment emergent adverse events deemed to be related to the device
- All other adverse events

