27.6 Safety Evaluation and Reporting

The sponsor is responsible for the classification of adverse events and ongoing safety evaluation of the clinical investigation and shall:

- a) review the investigator's assessment of all adverse events and determine and document in writing their seriousness and relationship to the investigational device; in case of disagreement between the sponsor and the principal investigator(s), the sponsor shall communicate both opinions to concerned parties,
- b) review all device deficiencies and determine and document in writing whether they could have led to a serious adverse device effect; in case of disagreement

CONFIDENTIAL

between the sponsor and the principal investigator(s), the sponsor shall communicate both opinions to concerned parties,

c) report or ensure the reporting, to the IRB by the principal investigator(s), of all serious adverse events and device deficiencies that could have led to a serious adverse device effect, if required by national regulations or by the IRB,

d) report to regulatory authorities, within the required time period, all serious adverse events and device deficiencies that could have led to a serious adverse device effect, if required by national regulations,

e) report all relevant safety information to the DSMB, if established, according to written procedures,

f) in the case of a multicenter clinical investigation, inform all principal investigators in writing of all the serious adverse device effects at all investigation sites that have been reported to the sponsor, and ensure that they are reported to their EC, if required by national regulations or by the IRB, whichever is more stringent,

g) ensure that the IRB and the regulatory authorities are informed of significant new information about the clinical investigation, and

h) in case of serious adverse device effects and device deficiencies that could have led to serious adverse device effects, determine whether the risk analysis needs to be updated and assess whether corrective or preventive action is required.

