4.2. Endpoints

The data from this clinical investigation will be based on the investigator / site reported information.

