14.2. Analysis of Adverse Events

The results of the safety analyses will be presented as described in the SRS TLF, Tables 40 through 44. These include summary statistics (as described in Section 8) of the following safety attributes:

- Overall summary of adverse events
- Adverse events related to the study device or study procedure
- Adverse events related to the study device or study procedure by study visit
- Serious adverse events
- Discontinuations from study participation

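### The protocol separates procedure-related from device-related adverse events, but the SAP text collects only device relatedness and tabulates the two together

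*SAP*

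**What the plan says.** Protocol 14.6 lists three safety variables:

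- "Treatment emergent adverse events deemed to be related to the implantation procedure"
- "Treatment emergent adverse events deemed to be related to the device"
- "All other adverse events"

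SAP 14.1.1 sets out the items obtained for each event (dates, severity, seriousness, action taken, outcome and so on). On causality it has only "relationship to the investigational device, whether anticipated or unanticipated per protocol definition". It then sends the reader to the protocol: "The definitions of seriousness, severity, relationship to device, and outcome are provided in the SRS Protocol". That sentence, too, mentions the device and not the procedure.

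SAP 14.2 lists the safety outputs. The one that uses causality is "Adverse events related to the study device or study procedure", given once overall and once by study visit.

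On who judges causality, SAP 4.2 states: "The data from this clinical investigation will be based on the investigator / site reported information". Protocol 26.8 has the investigator record each event with an assessment. Protocol 27.6 has the sponsor review that assessment and "determine and document in writing their seriousness and relationship to the investigational device". If the two disagree, both opinions are passed on to those concerned.

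**The concern.** Two of the three protocol safety variables are defined by causality, and they are kept apart. The SAP's list of collected items supports one of them, and its list of outputs merges them.

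The distinction matters here. Protocol 10.3 plans three stents for each of 105 subjects (105 × 3 = 315 planned placements), and protocol 12.1 schedules cystoscopy at Visits 1 and 4. Harm from placing a stent and harm from wearing one for about 30 days are different hazards. The protocol itself treats them so: section 21.5.3 separates passing haematuria caused by insertion trauma from persistent bleeding, which has to be investigated to see whether use of the stent is the cause. Protocol 7.4 attributes infection, bleeding and pain to cystoscopy, and similar effects appear in the list of anticipated device effects in 7.2.

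Assessing safety is one of the two stated aims of the statistical analysis (protocol section 9), and there is no control arm. How events are attributed is therefore a large part of what the safety tables can tell a reader.

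**Working it through.** The documents give no safety rate or target, so there is no figure to reproduce. The check is a comparison of the texts, followed by a bound that shows what a combined row can and cannot reveal.

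**Step 1. Variables against collected items.**

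| Protocol 14.6 variable | Needed for each event | Item in SAP 14.1.1 |
|---|---|---|
| Related to implantation procedure | Relationship to procedure | None listed |
| Related to device | Relationship to device | Listed |
| All others | Both of the above | Device only |

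**Step 2. Can the device item serve for both?** No. Note 1 to the adverse device effect definition (protocol 21.1.2) brings in events that come from inadequate deployment or implantation, and Note 2 adds user error. An assessor applying that definition would call at least some insertion injuries device-related, so a positive answer does not separate insertion from wear. Section 21 gives no causality categories that would do so.

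**Step 3. Can timing serve instead?** Not reliably. Protocol 12.1.1 asks for events during sizing and insertion at Visit 1 to be recorded, and SAP 14.1.1 obtains date and time of onset. At Visit 1, however, cystoscopy, sizing and placement take place at the same visit. At Visits 2 and 3 (protocol 12.1.2 and 12.1.3) one stent comes out and the next goes in. Onset time shows when an event began and does not show its cause.

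**Step 4. What does the combined output give?** Let D be the patients with a device-related event, P those with a procedure-related event, and U the number in the combined row.

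U = |D ∪ P| = |D| + |P| − |D ∩ P|

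Given U alone, the only bound is 0 ≤ |P| ≤ U, and the same holds for |D|. With the planned 105 enrolled as denominator and assumed values of U:

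- U = 10: |P| lies between 0 and 10, that is 0% to 10/105 = 9.5%.
- U = 20: |P| lies between 0 and 20, that is 0% to 20/105 = 19.0%.

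Neither of the first two protocol variables can be read from that row. At best the third can, by subtracting the combined count of events from the overall count.

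**Step 5. Whose assessment is tabulated?** SAP 4.2 points to the investigator or site. Protocol 27.6 adds a sponsor determination and keeps both opinions when they differ. Neither document says which one enters the tables. The sponsor's determination in 27.6 covers relationship to the device only, so this is a separate gap and does not cause the one in Steps 1 to 4.

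**The case against.** The strongest reply is that the detail may exist elsewhere. SAP 3.2 says that data variables are left to the table, listing and figure templates, and Attachment E gives the adverse event form (CRF21) by title only. SAP 14.2 could not plan a device-or-procedure table unless some judgement about the procedure were made. Protocol 14.6 promises that the variables will be recorded, not that each will have its own table. All events will be listed (protocol 14.8, SAP section 8). Safety is also descriptive here: success or failure of the trial turns on PVR alone.

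Much of this stands, and it limits the point. A reader might infer that procedure-related harm cannot be reported at all. The documents do not support that, because the form or the templates could hold a procedure item or split rows. What does not fall away is that the SAP sets out its own list of collected items and its own list of outputs, and both depart from protocol 14.6. Listings do not help if the causality item is not collected, and recording is exactly what 14.6 calls for.

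A reader might also see a direct conflict between investigator and sponsor judgement. The texts are compatible: the SAP 4.2 sentence is general and is followed only by effectiveness endpoints, and protocol 27.6 describes a review that preserves both views. Nothing there lets the sponsor overwrite the investigator's entry. What is missing is a rule for tabulation. Its effect cannot be sized, because the documents give neither an expected number of events nor a disagreement rate.

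Nor should 315 be read as a ceiling on placements. It is a planning estimate, and protocol 12.1.1 allows one replacement for incorrect sizing at Visit 1.

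**Conclusion.** The point holds in a limited form. As written, the protocol and SAP do not provide for separate reporting of procedure-related harm, although protocol 14.6 makes it a safety variable of its own. The gap comes from the missing item in SAP 14.1.1 and the merged output in SAP 14.2. The breadth of the adverse device effect definition means that the device item cannot fill it.

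The size depends on data not yet seen. If the combined row is all that is reported, the number of patients with a procedure-related event is known only to lie between zero and that row's count. The 10 and 20 patients used above are assumptions, not expectations for this trial. The conclusion also assumes that CRF21 and the templates contain nothing beyond what the SAP text describes. If they already hold a separate procedure item and split rows, only the SAP wording needs correcting.

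The primary endpoint, the sample size and the success rule are not affected. It should still be settled before the safety tables are programmed.

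**What to change.** - **Collection.** Add relationship to the implantation procedure to SAP 14.1.1, and to CRF21 if it is not already there. Keep it separable from cystoscopy and other study procedures. One item covering insertion, removal and cystoscopy together would not yield the variable in protocol 14.6.
- **Tables.** Split the SAP 14.2 causality outputs, overall and by visit, into device-related and procedure-related rows that match protocol 14.6. Count an event judged related to both in each row, and show the number judged related to both.
- **Assessor.** State that the investigator's assessment is tabulated as primary, in line with SAP 4.2, and show any differing sponsor assessment made under protocol 27.6 beside it.

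The cost is one added item on the adverse event form, if it is absent, and a few extra table rows. Visits, sample size and the effectiveness analysis stay as they are.

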14.1.2. Missing and Partial Adverse Event Dates

The recorded dates for adverse events are important for an accurate tabulation of both events and patients, and required for the following:

1. Defining the start of the event
2. Designation of unique adverse event occurrences recorded intra-patient.

Completely missing or partially missing adverse event dates will be imputed as follows, after due diligence to obtain accurate adverse event information has failed.

If the adverse event start date is completely missing the adverse event will be counted unless it can be determined that the adverse event end date occurred prior to the start of the study procedure. If the adverse event end date can be established as prior to the date of the study procedure, the adverse event will be considered as having occurred prior to the start of the study procedure and will not be counted.

If the adverse event start date is partially missing and the partial date is not sufficient to determine if the event occurred after the start of the study procedure, then the adverse event will be counted unless it can be determined that the adverse event end date occurred prior to the study procedure.

14.2. Analysis of Adverse Events

The results of the safety analyses will be presented as described in the SRS TLF, Tables 40 through 44. These include summary statistics (as described in Section 8) of the following safety attributes:

- Overall summary of adverse events
- Adverse events related to the study device or study procedure
- Adverse events related to the study device or study procedure by study visit
- Serious adverse events
- Discontinuations from study participation

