21.5 Managing Adverse Events and Device Deficiencies

CONFIDENTIAL

The following guidelines are recommended for managing Adverse Events and complications that may occur during the study. As these are only guidelines, the final decision for appropriate management of Adverse Events rests on the investigator's clinical judgment. Contact the SRS Medical for additional guidance on a case-by-case basis.

- If a device deficiency is known or suspected, The Spanner should be evaluated to determine if removal is necessary.
- If a device is removed in either in association with an adverse event or a device deficiency, then the subject is to attend the next scheduled visit.
- If the subject has no unresolved adverse events, then the subject should complete the study visit, including replacement of the stent and resume the study visit schedule.
- If the subject has unresolved adverse events, then complete as much of the study visit as possible, but do not place the stent. The subject should resume the study schedule and be reassessed at the next visit for the possibility of stent placement.

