5.3. Sample Size Justification

In order to have an 80% chance of showing that the success proportion in the Spanner group is statistically significantly greater than 50%, assuming that the device can achieve a 65% success rate, with a two-sided type 1 error rate of 5%, a sample size of $n=85$ completers will be needed for the study. Assuming that a one-sided type 1 error rate of 5% will be adequate, the sample size of 85 completers will provide 88% power. Completers are those subjects whose endpoint is known at 90 days.

Assuming a dropout rate of 20%, the total sample size of $n=105$ patients will be required for the study. Dropouts are those patients who exit the study prior to completing 90 days without experiencing a PVR failure. The sample size calculation was based on an exact binomial one sample test using PASS 14.0.9 (PASS 14 Power Analysis and Sample Size Software (2015). NCSS, LLC. Kaysville, Utah, USA, ncss.com/software/pass.)

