7. ANALYSIS POPULATIONS

The following populations will be considered for the summarization and analysis of the data from this study:

Intention to Treat Population

The Intention to Treat (ITT) population includes The ITT population will consist of any enrolled patient who underwent an attempted Spanner device implant procedure. This population will be used for all of the analyses unless otherwise stated.

Per Protocol Population

The Per Protocol (PP) population will consist of all patients who are enrolled in the study, have been implanted with a Spanner device, and have completed all study visits with no major protocol deviations while enrolled in the study. A major protocol deviation is defined as any protocol deviation that may affect the primary endpoint. The PP population will only be used as an analysis population if the ITT population produces unexpected results that could have been caused by protocol deviations.

Safety Population

The safety population will consist of all subjects who are enrolled in the study.

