8. ANALYSIS CONVENTIONS

Specific algorithms are discussed for imputing missing or partially missing dates, if deemed appropriate, under specific data topics. Imputed or derived data will be flagged in the individual patient data listings. Imputed data will not be incorporated into any raw or primary datasets. These data are retained in derived (or analysis) datasets.

Total duration on study will be calculated as the difference between the date of informed consent and the last on-study observation. All calculations defining the duration on study will be performed relative to the date of informed consent and follow the algorithm $DURATION = [STUDY\ COMPLETION\ OR\ WITHDRAW\ DATE - INFORMED\ CONSENT\ DATE]$.

General Conventions for Summarization

Summary statistics will consist of the number and percentage of responses or counts at each level for categorical variables (e.g. race). For continuous variables, and the sample size (n), mean, median, standard deviation (SD), minimum, and maximum values will be presented.

All mean and median values will be formatted to one more decimal place than the measured value. Standard deviation values will be formatted to two more decimal places than the measured value. Minimum and maximum values will be presented with the same number of decimal places as the measured value.

The number and percentage of responses will be presented in the form XX (XX.X%).

All probability values will be rounded to 4 decimal places; however, the number of digits to be displayed in the CSR tables will depend on the parameter and result. All probability values that round to 0.0000 will be presented as '<0.0001' and p-values that round to 1.0000 will be presented as '>0.9999'. Probability values < 0.05 will be considered to be statistically significant.

- All summary tables will include the analysis population sample size (i.e., number of patients).
- Relative Study Day 1 is defined as the day the patient underwent the initial study procedure. All study days are determined relative to the day the patient underwent the study procedure.
- Baseline values will be defined as those values recorded immediately prior to the study procedure.
- Change from baseline for ratio data will be calculated as follows:
$$\text{Change} = \text{Post-baseline value} / \text{baseline value}.$$
- Change from baseline for differences will be calculated as follows:
$$\text{Change} = \text{Post-baseline value} - \text{baseline value}.$$

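### SAP 14.2 gives related adverse events only as crude percentages, with no stated at-risk denominator or stent-time adjustment, so it can understate 90-day on-stent risk and cannot separate lower risk from less wear

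*SAP*

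**What the plan says.** SAP 14 states that "All safety results will be presented using the Safety population", and SAP 7 defines that set by enrollment alone: "The safety population will consist of all subjects who are enrolled in the study". SAP 14.2 then lists five safety attributes. They include related events overall and "Adverse events related to the study device or study procedure by study visit", each summarized by the Section 8 conventions: "Summary statistics will consist of the number and percentage of responses or counts at each level for categorical variables". Section 8 also requires each summary table to show the size of the analysis population, but it does not say what the denominator is at each visit. The table layouts (Tables 40 to 44) are in a separate TLF document that was not available for this review. Neither the protocol nor the SAP mentions stent-days, numbers at risk or a time-to-event estimate for adverse events.

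Four provisions make stent exposure unequal:

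- SAP 5.3 plans for 20% dropout and defines it narrowly: "Dropouts are those patients who exit the study prior to completing 90 days without experiencing a PVR failure". Withdrawals after a PVR failure come on top of the 20%.
- Protocol 21.5.8 withdraws men with PVR above 350 ml on two measurements.
- Under Protocol 21.5, a man whose stent is removed for an adverse event or device deficiency stays in the study and attends the next scheduled visit, where the stent may be replaced. Visits are 25 to 35 days apart.
- If an event is unresolved at that visit, the site is to "complete as much of the study visit as possible, but do not place the stent", and the man is reassessed one visit later.

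**The concern.** A crude percentage answers how many enrolled men had a related event under the regimen as delivered. It does not answer what the risk is for a man who wears the stent for 90 days, or whether the second and third stents carry the same risk as the first. The second question is new in this trial: Protocol 10.1 notes that current US labeling does not foresee replacing the first stent after 30 days. The by-visit table is the listed output closest to it.

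If fewer men wear a stent in months 2 and 3 and the denominator does not follow them, a falling percentage may reflect less wear and not lower risk. As planned, the tables give no means of telling these apart.

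**Working it through.** **The plan's own figure.** The only stated figure this point depends on is the 20% dropout behind N = 105. 85 / 0.80 = 106.25, so 107 men; conversely 105 × 0.80 = 84. The stated 105 is within two men of this, and the difference does not matter here.

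**Inputs.** 20% exit (SAP 5.3), three intervals of about 30 days (SAP 5.2), and N = 105. The documents give no adverse event rate, so the true 90-day on-stent risk R is assumed over 10% to 70%. Exit is assumed uniform over days 0–90 and unrelated to events.

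**Overall percentage, constant hazard.** With λ = −ln(1 − R)/90, the mean risk among men who exit is 1 − R/(−ln(1 − R)). The crude percentage is 0.8 × R + 0.2 × that mean. For R = 50%: 1 − 0.5/0.693 = 0.279, and 0.8 × 0.5 + 0.2 × 0.279 = 0.456.

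| True 90-day risk | Crude percentage | Ratio |
|---|---|---|
| 10% | 9.0% | 0.90 |
| 20% | 18.1% | 0.90 |
| 30% | 27.2% | 0.91 |
| 50% | 45.6% | 0.91 |
| 70% | 64.4% | 0.92 |

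The shortfall is 1.0 to 5.6 points, or about 8–10% relative.

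**Overall percentage, early events.** If all the hazard falls in the first 30 days, only the one-third of exits in that month lose risk time. For R = 50%, the mean among men who exit is (1/3) × 0.279 + (2/3) × 0.5 = 0.426. The crude percentage is 0.8 × 0.5 + 0.2 × 0.426 = 0.485.

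**Stent-free gaps.** These follow removal for an event, so they were simulated that way (400,000 men, one event type that triggers removal and one that does not, stent replaced at the next visit).

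| Setting | Any related event: true → observed | Non-triggering type: true → observed |
|---|---|---|
| Gaps, no dropout | 36.0% → 36.1% | 20% → 19.5% |
| Gaps, no dropout | 51.0% → 50.9% | 30% → 28.6% |
| Gaps, 20% dropout | 51.0% → 46.5% | 30% → 26.0% |

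Gaps alone leave the any-event figure unchanged apart from simulation error, because the man already counts. They lower the by-type figure.

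**By-visit percentages, if the denominator is all 105.** The average fraction still in the study in interval k is 1 − 0.2 × (k − 0.5)/3, which is 0.967, 0.900 and 0.833 (101.5, 94.5 and 87.5 men). A 50% risk over 90 days at constant hazard is 1 − 0.5^(1/3) = 0.2063 per 30 days.

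| Share of remaining men off stent in months 2 and 3 (assumed) | Month 1 | Month 2 | Month 3 | Fall, month 1 to 3 |
|---|---|---|---|---|
| 0% | 19.9% | 18.6% | 17.2% | 1 − 0.833/0.967 = 14% |
| 10% | 19.9% | 16.7% | 15.5% | 1 − 0.750/0.967 = 22% |
| 20% | 19.9% | 14.9% | 13.8% | 1 − 0.667/0.967 = 31% |

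The true monthly risk is constant in every row.

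**The case against.** Several objections have force.

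- **The by-visit denominator is not known.** SAP 14 and Section 8 suggest the full Safety population, but the TLF could already use men seen at each visit. This stands, so the by-visit figures are conditional.
- **Exits may follow events.** Elevated PVR is a listed device effect (Protocol 7.2) and retention is recorded as an adverse event (Protocol 21.5.6). Men withdrawn for these reasons will often already count, and the overall shortfall then shrinks towards zero. This also stands.
- **Some rules push the other way.** Events are collected for up to 125 days, and events whose dates do not settle the matter are counted as treatment emergent.
- **The crude percentage is a valid description** of experience under the regimen, apart from men lost to follow-up. The trial has no safety hypothesis and no objective comparing first with later stents. The SAP also plans numbers evaluated per visit, discontinuations and full listings. That is a reason to keep the crude table; none of these outputs supplies a rate per unit of wear.

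A reader might go further and infer that the 90-day device risk is definitely understated, partly because men spend time without a stent. The documents do not support that. Under Protocol 21.5 gaps follow an adverse event or a deficiency, and Protocol 21.1.1 requires deficiencies to be reported as adverse events, so these men normally already count overall if the event is judged related. A reader might also infer that a man without a stent cannot contribute an event. The table covers procedure-related events too, and a stent removed mid-interval was worn for part of it. Nor do the documents give any off-stent share, so a month-3 figure one-quarter below the true risk (15.5% against 20.6%) rests on an assumed 10% off stent in addition to dropout.

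**Conclusion.** The concern holds as a limitation of the planned tables, not as a demonstrated bias. The crude overall percentage can understate the 90-day on-stent risk, by about 8–10% relative under constant hazard and non-informative uniform 20% exit, and by less if events come early or exits follow them. Stent-free gaps matter mainly for the by-visit and by-type percentages. If the by-visit table divides by all enrolled men, dropout alone would produce an apparent fall of about 14% from month 1 to month 3 with no change in risk, and more if some men are off stent. All these sizes rest on an assumed event rate and exit pattern. What does not depend on them is that the planned outputs cannot distinguish lower risk from less wear with the second and third stents. It should be fixed before analysis.

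**What to change.** In SAP 14.2, keep the crude table and add:

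1. By-visit percentages whose denominator is the men with a stent in place for any part of that interval, with the number at risk printed.
2. Device-related adverse events per 30 stent-days with a 95% confidence interval, overall and by stent number (first, second, third), using an interval that allows for repeated events in one man.
3. The 90-day cumulative incidence of first device-related adverse event, stating whether early exit is treated as censoring or as a competing event. Withdrawals for PVR should be addressed explicitly, since censoring them assumes they are unrelated to risk.

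Most inputs should exist. SAP 14.1.1 collects event onset dates, and Protocol 15.1 requires the eCRF to capture device exposure. SAP 12.3 and 12.4 tabulate insertion and removal but do not mention dates, so confirm that the eCRF records both dates, including unscheduled removals. The cost is SAP wording, a few tables and possibly a less favourable reported risk.
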